## **7.8. Interim Analyses**

No interim analyses have been planned.

## 7.9. Evaluation of Objectives

### 7.9.1. Primary Endpoint

The Primary Endpoint of the Study is to quantify the incidence of RC markers in high risk postsurgical patients, using a system comprised of two continuous monitoring devices, connected to a remote monitoring platform. The proportion and rate of “At least one RC marker” event will be calculated and reported.

The “At least one RC marker” event is defined as the occurrence of at least one of the following RC markers:

1.  $\text{SpO}_2 \leq 90\%$  for  $\geq 3$  minutes (or  $\text{SpO}_2 \leq 90\%$  for  $< 3$  min with an action taken);
2.  $\text{RR} \leq 8$  or  $\geq 22$  bpm for  $\geq 3$  minutes (or  $\text{RR} \leq 8$  or  $\geq 22$  bpm for  $< 3$  min with an action taken);
3.  $\text{EtCO}_2 \leq 15$  or  $\geq 60$  mmHg for  $\geq 3$  minutes (or  $\text{EtCO}_2 \leq 15$  or  $\geq 60$  mmHg for  $< 3$  min with an action taken);
4. Apnea episode lasting  $> 30$  seconds.

For patients monitored by PM1000N, only RC markers #1 and #2 will be considered.

RC determination will be assessed by a physician belonging to the “other” site (cross assessment by the sites). This assessment will be made by the analysis of both device and clinical data for each patient. For each patient all potential RC episodes will be derived using the Detection Tool (see Section 10.1) and will be submitted to the other site’s physician in order to adjudicate the potential RC episodes starting from episodes most likely to be RC. The adjudication will stop at the first RC occurring per patient.

The Events’ rates will be computed as (total number of “At least one RC marker” event)/(total number of time-person in PPS) and will be reported separately for each arm and phase of the study. Events’ rates will be displayed together with their 95% confidence interval (95%CI).

If the number of episode per patient result unbalanced, adjusted rates will be reported using the GEE model, together with their 95% confidence interval (95%CI).

If appropriate, also the events’ rates for each RC marker will be reported separately, for each arm and phase of the study.

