## 4. Objectives and Endpoints

### 4.1. Objectives

#### 4.1.1. Primary Objective and Endpoint

The primary objective of this study is to quantify the incidence of RC markers in high risk postsurgical patients, using a system comprised of two continuous monitoring devices, connected to a remote monitoring platform.

The occurrence of at least one of the following RC markers will be considered as primary endpoint for patients monitored by Capnostream 20p during both study Phases:

1. SpO2 ≤ 90% for ≥ 3 minutes.
2. RR ≤ 8 or ≥ 22 bpm for ≥ 3 minutes.
3. etCO2 ≤ 15 or ≥ 60 mmHg for ≥ 3 minutes.
4. Apnea episode lasting > 30 seconds.

The occurrence of at least one of the following RC markers will be considered as primary endpoint for patients monitored by PM1000N-RR during both study Phases:

1. SpO2 ≤ 90% for ≥ 3 minutes.
2. RR ≤ 8 or ≥ 22 bpm for ≥ 3 minutes.

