## 8.10 Recording Data

The investigator will clearly mark the clinical records to indicate that the patient is enrolled in this clinical study. The patient's medical records will be used as source documents. Worksheets may serve as source documentation in particular cases if a data field is not in the patient's medical record. Details will be specified in the Monitoring Plan and specific guidance will be provided depending on the site practice.

Capnostream™ 20p or Nellcor Monitoring Systems' device memory data will be the source for the number and duration of RC markers. Device memory data will be exported to a flash memory device for each patient. The memory device will be stored at the investigation site. Device memory data will subsequently be downloaded and transferred to a secure server at Medtronic.

The device data transfer process will be tested and verified during the site initiation process. This will be completed to ensure data quality and identify any process improvements to maximize quality, as needed.

The investigator must ensure accuracy, completeness and timeliness of the data reported in the eCRFs and in all other required reports. Data reported on the eCRFs which are derived from source documents, such as patient medical records, must be consistent with the source documents or the discrepancies need to be justified in a documented rationale, signed and dated by the (principal) investigator, to be filed in the patient file. All baseline and medical history data must be derived from source documents.

Only authorized persons can complete eCRFs. Training will be provided to site personnel on the use of data collection tools. CRFs shall be electronically signed by investigators (physician) or by authorized site staff as specified on the Delegated Tasks List. The final version of eCRFs will be provided to the investigation sites when the investigational site has been declared ready for the study.

It is expected that eCRF will be completed within 15 days from the performed visit or as soon as source documents are available, except for Serious Adverse Events that require immediate reporting (see Table 3) and for Protocol Deviation requiring pre-approval. A delayed completion of the eCRF will not be considered a Protocol Deviation.

Sponsor study personnel will review all collected data and create data queries for missing data that impacts data analysis. Queries will be sent to the investigator or appropriate support staff for resolution.

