## 11. Clinical Event Committee

This study will not have a Clinical Event Committee (CEC).

Since only two German sites will be involved, assessment of study specific endpoints and/or events will be performed by delegated site sub-Investigators that will perform cross-site events assessment

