### **10.1. Detection Tool**

The Detection Tool analyzes each patient's monitoring using an algorithm based on the device episodes thresholds as stated in the primary endpoint. The Detection Tool provides for each patient multiple Episodes. Since there could be multiple episodes in a short time period around each Episode, the Detection Tool is set to aggregate episodes with at most 30 minutes time difference between them in one file. In addition, the episodes file consists of time window of 30 min before and after the first and last episode.

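### The SAP passes device-detected episodes through an unmasked physician review with no device-only result beside it, so the phase comparison can partly reflect phase-dependent acceptance

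*SAP*

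**What the plan says.** **CIP.** Section 4.1.1 defines the endpoint by thresholds and durations alone: "The occurrence of at least one of the following RC markers will be considered as primary endpoint for patients monitored by Capnostream 20p", with a shorter marker list for PM1000N-RR. Section 8.10 says that "device memory data will be the source for the number and duration of RC markers". Section 11 provides no Clinical Event Committee; instead "assessment of study specific endpoints and/or events will be performed by delegated site sub-Investigators", working across sites.

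**SAP.** The Detection Tool (Section 10.1) finds candidates "using an algorithm based on the device episodes thresholds as stated in the primary endpoint". Under Section 7.9.1 these go to the other site's "physician in order to adjudicate the potential RC episodes starting from episodes most likely to be RC". The evidence is wider than the device record: "This assessment will be made by the analysis of both device and clinical data for each patient". One accepted episode settles the patient: "The adjudication will stop at the first RC occurring per patient". SAP 4.1 and 7.9.1 also count SpO2, RR and etCO2 episodes shorter than 3 minutes if an action was taken. CIP 4.1.1 has no such clause.

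**Use of the result.** SAP 7.9.2 compares the phases on this endpoint (secondary endpoint #1) by chi-square or Fisher exact test, with a Poisson rate ratio if exposure differs. SAP 7.2 sets a two-sided 0.05 level.

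**Not stated.** Neither document lists what the adjudicator receives, describes masking to phase, alarms or staff actions, gives criteria for rejecting an episode that meets the thresholds, or plans a device-only proportion beside the adjudicated one.

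**The concern.** A device-recorded threshold crossing does not depend on who looks at it. Acceptance by a physician does. The phases are not randomised against each other; only the device is. An outcome free of judgement is therefore one of the few protections the phase comparison has.

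If adjudicators accept candidates more readily in one phase than in the other, the confirmed proportions differ even when the device-detected proportions do not. Without a device-only result, a reader cannot tell how much of a phase difference arose at adjudication.

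**Working it through.** **Step 1: can the adjudicator infer phase?** Set the CIP provisions side by side.

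- Section 5: alarms are silenced and screens blinded in Phase I only. The phases run in sequence, at least one month apart, so calendar dates separate them.
- Section 4.1.2: alarm-triggered interventions are expected only in Phase II.
- Section 8.7: alarm thresholds are collected in Phase II only. Alarm classification and action taken on an alarm are also eCRF items, and with silenced alarms they have no content in Phase I.
- SAP 4.1 and 7.9.1: the action clause cannot be applied without data on staff actions.

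Clinical data of this kind would usually show the phase. The documents do not say that phase is shown.

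**Step 2: inputs.** The plan gives no adjudication error rates and no power for the phase comparison, so there is no figure of its own to reproduce.

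- Evaluable patients, from the SAP Section 6 attrition rates (10% and 5%): 70 × 0.90 × 0.95 = 59.9 and 140 × 0.90 × 0.95 = 119.7, taken as 60 and 120.
- Candidate incidence c, the proportion of patients with at least one candidate episode, equal in both phases: 10% (the planning proportion in SAP Section 6), and 50% and 80% (assumed).
- Acceptance k (assumed): 90% in Phase I; 85, 80 or 75% in Phase II. Making Phase II the lower one is for illustration only.

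**Step 3: formula.** With one candidate per patient, adjudicated incidence is c × k. For x of 60 and y of 120 confirmed, and p = (x + y)/180,

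z = (y/120 − x/60) / √[p(1 − p)(1/60 + 1/120)],

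and the test rejects when |z| > 1.96. The rejection probability is the sum of the two binomial probabilities over all (x, y) that reject (uncorrected chi-square, exact enumeration).

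Hand check at c = 50%, acceptance 90% v 80%: incidence 45% v 40%; p = (27 + 48)/180 = 0.417; standard error = √(0.417 × 0.583 × 0.025) = 0.078; shift = 0.05/0.078 = 0.64. The normal approximation is P(Z > 1.32) + P(Z < −2.60) ≈ 9.8%, against 9.9% by enumeration.

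**Step 4: false rejection with no true phase difference**

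| Candidate incidence | 90% v 90% | 90% v 85% | 90% v 80% | 90% v 75% |
|---|---|---|---|---|
| 10% | 5.2% | 5.6% | 6.3% | 7.3% |
| 50% | 5.0% | 6.2% | 9.9% | 16.3% |
| 80% | 5.1% | 8.3% | 18.6% | 35.4% |

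**Step 5: several candidates per patient.** One acceptance suffices, so with m independent candidates the confirmed share is 1 − (1 − k)^m. For m = 3 and 90% v 75%: 1 − 0.1³ = 99.9% v 1 − 0.25³ = 98.4%. At c = 50% false rejection falls to 5.2%. If one physician's judgements on the same patient are correlated, the protection is weaker.

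**Step 6: the action clause.** This is a separate route. In Phase II the settings suggested in CIP Appendix B alarm after 30 seconds, so staff may act on episodes under 3 minutes that blinded screens would have hidden in Phase I. Such episodes can then count in Phase II more often than in Phase I, whatever the adjudicator expects. A device-only proportion without the clause would show this as well.

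**The case against.** **The SAP keeps the CIP endpoint.** A reader might infer that adjudication replaces it. The documents do not support that: every CIP threshold remains, the thresholds generate the candidates, and CIP Section 11 already assigns endpoint assessment across sites. What the SAP adds is a filter and an action clause, and CIP 4.1.1, 8.10 and 11 do not describe either.

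**Knowledge of phase is not documented.** A reader might infer that adjudicators are told the phase and see alarm logs. The SAP says only device and clinical data. The supported statement is that no masking is described and that phase is easy to infer.

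**The effect may be small.** A reader might equate acceptance gaps of 5, 10 or 15 points with equal gaps in incidence. Incidences of 50% v 55, 60 or 65% would be declared different in 9.8, 24.8 or 49.0% of studies, but those are gaps in patient incidence. A filter can only remove candidates, and at 50% candidate incidence a 10-point acceptance gap moves incidence by 5 points. At the planning proportion of 10% the inflation is slight, and several candidates per patient shrink it further. This stands.

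**The scope is narrow.** The primary analysis is descriptive, the study is a pilot, and the affected test is secondary and non-randomised. Nobody judges their own site's patients. Clinical context also helps to reject artefact, such as the talking, eating or compressed sensor in CIP 8.7. This stands too, but it does not explain the absence of a device-only result.

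**Conclusion.** The point holds in a limited form. Judgement based on clinical data stands between the device record and the endpoint, no masking or rejection criteria are described, and nothing planned would show how much of a phase difference comes from adjudication. Secondary endpoint #1 is the test exposed; the descriptive proportions by arm and phase also carry the filter.

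Under the assumed acceptance rates the false rejection rate runs from 5.6% (10% candidate incidence, 5-point gap) to 35.4% (80%, 15-point gap), against about 5% with equal acceptance. The range rests on 60 v 120 evaluable patients, one candidate each and no true phase difference. The real acceptance rates, the number of candidates per patient and the direction of any bias cannot be taken from the documents. The result supports a change to reporting, and masking where feasible. It does not show that the phase comparison will be wrong.

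**What to change.** 1. **Report a device-only result.** By arm and phase, with 95% confidence intervals, give the proportion of patients meeting the CIP thresholds and durations from device memory alone, without the under-3-minute action clause, beside the adjudicated proportion. Repeat the phase comparison on it. This uses data already recorded. The cost is a small amount of programming, including separating CIP-duration episodes from the shorter action episodes if the Detection Tool output does not already do so.
2. **Mask where feasible.** Give adjudicators episode files without calendar date, phase, alarm log or staff actions, in random order across both phases, and apply the action clause by program afterwards. The cost is redaction work, later adjudication (Phase II files must exist before the phases can be mixed), some lost context for rejecting artefact, and masking that is only partial.

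The SAP should also list what the adjudicator receives and on what grounds an episode that meets the thresholds may be rejected, and reconcile this with CIP 4.1.1, 8.10 and 11.

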## 8.7 Monitoring Period

Continuous monitoring from either Capnostream™ 20p or Nellcor Monitoring Systems will be performed on all patients for a minimum of 24 hours. The monitoring period will last up to patient's full mobilization or up to a maximum of 72 hours, if the patient is still bed-ridden after two days post-surgery.

The monitoring period will start for patients once they arrive on the ward. For patients who are determined to be at high risk due to opioid therapy and not due to other pre-existing factors, monitoring of capnography and pulse oximeter data will start only after opioid therapy has been initiated.

Monitoring may be discontinued if the patient is discharged from the hospital ward.

During Phase I the alarm feature of the monitoring devices will be silenced and the screen information blinded. A regular check during the monitoring period should be completed to ensure the etCO2 filter line and SpO2 sensors are appropriately fitted on the patient.

During Phase II the medical staff will be instructed to respond to alarm feature of the monitoring devices and their screen will be open. A guideline will be created to instruct the nurses in responding to alarms and changes in the monitored parameters. An alarm will be considered a false positive by the observer if the SpO2 sensor or the etCO2 filter line is off the patient or misplaced. Alarms will be considered true positive if the SpO2 sensor and etCO2 filter line placement is correct: observations on patient activity and subsequent interventions will be recorded in the eCRF to identify clinically significant or insignificant alarmed events. As an example, patient activities such as talking, eating or gripping a book with the SpO2 sensor compressed will be marked as true positive with details of the activity recorded to identify the alarmed event as potentially clinically insignificant if no medical intervention was taken. The Monitoring eCRF will be completed to document:

- Care pathway (location/transfer within hospital)
- Alarm threshold applied to the monitor (to be collected during the Monitoring Phase II only for each measured parameter, PR, RR, SpO2 and EtO2).
- Systolic blood pressure and level of consciousness using the AVPU scale to allow the retrospective NEWS analysis
- Monitoring duration
- Vital signs
- Supplemental oxygen use
- Medications
- Product information

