## 5.3. Overall study design and plan-description

Subjects will be randomly allocated 1:1 to either Capnostream™ 20p or Nellcor Monitoring Systems both in Phase I and in Phase II. The device allocation will be unblinded to both subject and physician.

Continuous monitoring from either Capnostream™ 20p or Nellcor Monitoring Systems will be performed in all subjects for a minimum of 24 hours. The monitoring period will last up to patient's full mobilization or up to a maximum of 72 hours, if the subject is still bed-ridden after two days post-surgery.

During Phase I the alarm feature of the monitoring devices will be silenced, and the screen information blinded. A regular check during the monitoring period should be completed to ensure the EtCO2 filter line and SpO2 sensors are appropriately fitted on the subject.

During Phase II the medical staff will be instructed to respond to alarm feature of the monitoring devices and their screen will be open. A guideline will be created to instruct the nurses in responding to alarms and changes in the monitored parameters on which the nurses will be trained on.

A Flow-chart to schematize the disposition of subjects during the study is presented in Figure 1.

Capnography and pulse oximetry monitoring device data will be collected as well as clinical data related to respiratory compromise. Subjects will be monitored per standard of care.

[figure not shown]
Enrollment at any single site will be limited to 50% (approximately 105 subjects) to ensure poolability of the data across sites and reduce potential bias. Additional methods incorporated to minimize potential bias include the following:

- Systematic identification of potential subjects via screening;

[figure not shown]
- Standard procedures and data collection requirements with a common electronic database for all sites;
- Random allocation to monitoring device.

Foreseeable factors that may compromise the outcome of the study include lack of enrollment or the lack of RC events.

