### 7.9.2. Secondary Endpoints

The secondary endpoints are:

1. To compare phases in terms of Primary endpoint incidence;
2. To compare phases in terms of respiratory and SAE incidence, number of ICU transfers and related length of stay, Code blues and RRT responses.
3. To evaluate the rate of clinical early interventions performed by nurse staff to prevent a potential AE, introducing continuous monitoring devices connected to a remote monitoring platform;
4. To evaluate the nurses’ satisfaction related to the monitoring system introducing continuous monitoring devices connected to a remote monitoring platform;
5. To establish the Predictive values of  $\text{EtCO}_2$ , RR,  $\text{SpO}_2$ , plethysmography-derived RR, IPI and EWS in respect to respiratory and other SAE.

In order to evaluate secondary **endpoints #1 and #2**, the incidence of events will be reported together with the comparison between phases, by means of the Chi-square test or Fisher exact test for extreme

proportions, as appropriate. If the monitoring/study exposure results different between phases, also the rates of events will be reported, together with the 95% Poisson Confidence Intervals. The Poisson regression model will be used to calculate the Incidence Rate ratio (IRR), with the d-scale option.

For **endpoint #3**, the rate of clinical early interventions will be calculated as (number of early interventions)/(total time-person in FAS) and it will be reported together with the 95% Poisson Confidence Interval.

Early interventions include, as defined in CRF (Monitoring Period):

1. Stimulated subject to breathe;
2. Repositioned/opened airway;
3. Held or reduced Respiratory Depressive (RD);
4. Added or increased supplemental oxygen;
5. Ventilation support;
6. Other

**Endpoint #4** will be evaluated reporting a summary of the nurses' satisfaction answers.

To identify the predictive values for EtCO2, RR, SpO2, plethysmography-derived RR, IPI and EWS, which can predict respiratory and other SAE, a sensitivity analysis will be performed (**endpoint #5**), and the following parameters will be reported, for each RC marker:

1. **Sensitivity** = 
$$\frac{(\# \text{ of clinical events "Yes" and with RC marker "Yes"})}{(\# \text{ of clinical events "Yes"})} = \frac{TP}{(TP+FN)}$$
2. **PPV** = 
$$\frac{(\# \text{ of clinical events "Yes" and with RC marker "Yes"})}{(\# \text{ of events with RC marker "Yes"})} = \frac{TP}{(TP+FP)}$$

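### SAP 7.9.1 and 7.9.2: the RC rate sets a one-per-patient count against person-time with no stated end at the event, and no planned endpoint #1 phase comparison is aligned in time

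*SAP*

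**What the plan says.** **Numerator.** Under SAP 7.9.1 a physician at the other site is to "adjudicate the potential RC episodes starting from episodes most likely to be RC". Then: "The adjudication will stop at the first RC occurring per patient". Each patient therefore adds 0 or 1.

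**Denominator.** The same section divides this count by the "total number of time-person in PPS", by arm and phase. It does not say whether a patient's time ends at the event. The only exposure formula, in SAP 7.7, runs from start to end of monitoring. A footnote to SAP 7.1.3 defines effective time (valid recorded time) but does not tie it to the rate.

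**GEE.** SAP 7.9.1 also plans GEE-adjusted rates if the number of episodes per patient is unbalanced.

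**Phase comparison.** For endpoints #1 and #2, SAP 7.9.2 tests incidence between phases by chi-square or Fisher, and adds: "If the monitoring/study exposure results different between phases, also the rates of events will be reported". Further: "The Poisson regression model will be used to calculate the Incidence Rate ratio (IRR), with the d-scale option". The offset is not stated.

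**Length of monitoring.** SAP 5.3 sets at least 24 h, then until "full mobilization or up to a maximum of 72 hours". Protocol 8.7 adds: "Monitoring may be discontinued if the patient is discharged from the hospital ward".

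**Primary analysis.** Protocol 12.3 reports the proportion of patients with at least one RC marker and names the FAS. SAP 7.9.1 reports both proportion and rate, and SAP 7.1.3 assigns the primary endpoint and secondary endpoint #1 to the PPS.

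**The concern.** A first-event rate stops each patient's clock at the event. A recurrent-event rate counts every event. The 7.9.1 rate, on its natural reading, does neither: a patient whose one countable RC has been confirmed keeps adding time and can add no further event. The GEE sentence presupposes several counted episodes per patient, which the stopping rule excludes.

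Because episodes are reviewed in order of likelihood, the confirmed RC need not be the earliest. The time of the first RC may then be unknown, and ending time at the confirmed episode would not repair the rate.

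What is at stake is the comparison of phases. The rate ratio is brought in when exposure differs between phases, which is when this rate is distorted. Two phases with the same RC risk could show different rates because patients in one of them mobilised or left the ward sooner. Separately, the d-scale option sets the variance from the deviance, and for a 0/1 outcome that deviance does not estimate dispersion.

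**Working it through.** **Inputs.** From the documents: 70 and 140 patients, monitoring of 24 to 72 h, planning proportion 10% (SAP 6). Assumed: 10% read as 24 h risk; 37% and 63% as illustrations of common RC; the same hazard in both phases; mean monitoring times, which the documents do not give. The SAP states no numeric rate to reproduce. Its only related figure is 182 evaluable patients: at 10%, an exact 95% interval with half-width of at most 5 points reaches probability 0.80 at n = 179 and has 0.855 at 182.

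**1. The rate against monitoring length.** With constant hazard λ = −ln(1−p24)/24, the SAP rate at monitoring time T is (1−e^(−λT))/T. At p24 = 10% it is 10.0, 9.5 and 9.03 per 100 patient-days at 24, 48 and 72 h. Ending time at the first event, or counting all events, gives 10.54 at every T. As a share of λ:

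| 24 h risk | 24 h | 48 h | 72 h |
|---|---|---|---|
| 10% | 0.95 | 0.90 | 0.86 |
| 37% | 0.80 | 0.65 | 0.54 |
| 63% | 0.63 | 0.43 | 0.32 |

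**2. The rate ratio when the truth is 1.00.** The risk by T is 1−(1−p24)^(T/24). For 36 v 48 h the ratio is (risk at 48 h/48)/(risk at 36 h/36):
- 10%: (0.190/0.146) × 0.75 = 0.975
- 37%: (0.603/0.500) × 0.75 = 0.905
- 63%: (0.863/0.775) × 0.75 = 0.835

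Simulation with monitoring spread ±12 h around each mean gives 0.97, 0.91 and 0.84. For 42 v 48 h it gives 0.99, 0.95 and 0.92. For 36 v 60 h, an extreme contrast, it gives 0.95, 0.82 and 0.71.

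**3. The d-scale alone (equal monitoring, 36 v 36 h).** For a 0/1 outcome with risk P, the Poisson deviance per patient is about −2P ln P, whereas the true variance is (1−P) times the mean. The false-positive rate is about 2[1−Φ(1.96/k)], with k = √[(1−P)/(−2P ln P)].

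| 24 h risk | P at 36 h | d-scale | True factor | k | False positives |
|---|---|---|---|---|---|
| 10% | 0.146 | 0.562 | 0.854 | 1.23 | 11% |
| 37% | 0.500 | 0.693 | 0.500 | 0.85 | 2% |
| 63% | 0.775 | 0.395 | 0.225 | 0.75 | 1% |

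Simulation agrees: 11, 2 and 1%.

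**4. Both together (36 v 48 h, 70 v 140, constant hazard, no phase effect).** The d-scaled interval excludes 1 in about 10, 6 and 48% of trials. At 10% risk this is no more than the 11% in step 3, and robust variance on the same uncut rate gives 4–5%. Ending time at the first RC with robust variance gives 4–5% throughout.

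**5. The planned chi-square test, same setting.** The whole-monitoring proportion differs significantly between phases in about 13, 32 and 38% of trials, because longer monitoring gives more chance of an RC.

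**6. Other hazard shapes.** With a rising hazard (Weibull shape 2), 10% risk and 36 v 48 h, the SAP ratio is about 1.2. With a steeply declining one (shape 0.5) it is 0.86, and ending time at the first RC moves it only to 0.87. Under constant and declining hazards (shapes 1, 0.7 and 0.5), the 24 h incidence comparison rejects in 5–7% of trials.

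**The case against.** **The denominator is inferred.** The SAP does not say that person-time continues after the event, nor what the offset is. That stands. It is the natural reading, given the word total, the absence of a stopping rule and the formula in SAP 7.7, but the rate-ratio part is conditional on it. The missing rule needs writing in any case.

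**The rate need not fall as monitoring lengthens.** A reader might infer that it always does. It does so under a constant or declining hazard; step 6 shows that a rising hazard can reverse the direction.

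**At the planning figure the denominator does little.** A reader might blame it for the 10% false positives in step 4. They come from the d-scale.

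**The rate partly corrects for exposure.** This also stands: at 36 v 48 h and risks of 10% and 37%, the chi-square test is more sensitive to monitoring length than the rate ratio is. At 63% the order reverses. Dropping the rate and relying on the proportion would therefore not solve the problem.

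**Side issues.** The d-scale may suit the endpoint #2 counts; the criticism is confined to endpoint #1. For endpoint #3, interventions can repeat within a patient, yet the plan says "it will be reported together with the 95% Poisson Confidence Interval". The loss of coverage depends on a dispersion that the documents do not give. The effect of the PPS dropping patients with less than 24 h likewise depends on who leaves early, so no size is claimed for either.

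**Conclusion.** Wrong as written, and minor. The 7.9.1 rate has no clear estimand, the GEE sentence contradicts the stopping rule, and the d-scale is unsuitable for the 0/1 outcome of endpoint #1 even with equal monitoring. At 10% risk the denominator bias is about 3% for 36 v 48 h. It reaches roughly 9% and 16% only at 24 h risks of 37% and 63%. These sizes rest on constant hazard, assumed monitoring times and an offset equal to the 7.9.1 person-time.

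Common RC cannot be excluded. Protocol 3.1 cites up to 37% of patients with saturation below 90% for over an hour, and the endpoint needs only 3 minutes at or below 90%, whereas the planning data used 85%. But that 37% is not given as a 24 h risk or as an adjudicated figure.

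A reader might infer that the primary result is invalid. The documents do not support this: the protocol's primary analysis is the proportion, which does not use the person-time denominator. The broader conclusion that holds is that neither the proportion test nor the rate ratio compares the phases over the same length of monitoring.

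**What to change.** 1. Adjudicate in time order, or after a confirmation review the earlier episodes, so that the earliest confirmed RC is known. At the least, establish whether one occurred in the first 24 h.
2. Add the cumulative incidence of first RC at 24 h, by arm and phase, as the time-aligned comparison for endpoint #1. Keep the whole-monitoring proportion as the protocol's primary analysis and state that it depends on monitoring length.
3. If a rate or rate ratio is reported, define person-time and the offset, end each patient's time at the earliest confirmed RC, and use robust variance instead of the d-scale for endpoint #1. State that the result is free of monitoring length only under constant hazard.
4. Delete the GEE sentence, or adjudicate all episodes and report a recurrent-event rate.
5. Repeat the 24 h incidence in the FAS, censoring at the end of monitoring, since Protocol 12.3 names the FAS. This needs the time of the first RC.
6. Optional: a patient-clustered interval for the endpoint #3 rate.

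**Cost.** SAP wording, programming and some extra review by the same adjudicators, in an amount that the documents do not allow to be estimated; likelihood order is quicker for the yes/no endpoint. The 24 h measure ignores later RCs, which the proportion still counts. Censoring in the FAS assumes that patients who leave early without an RC have the same later risk as those who stay. The adjudication order should be settled before adjudication begins.
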